1.0 Study Summary

Study Title	Evaluation of Contraception Care @ Behavioral Health Pavilion
Study Design	Longitudinal Survey Study
Primary Objective	
 1. Examine interest in receiving contraception counseling among female adolescents hospitalized with mental health disorders. 2. Examine contraception initiation among female adolescents hospitalized with mental health disorders
Secondary Objective(s)	Examine associations between short- and medium-term outcomes and predictor variables among female adolescents with mental health disorders
Research Intervention(s)/ Investigational Agent(s)	The protocol here entitled “Evaluation of Contraception Care @ Behavioral Health Pavilion” describes how the investigators plan to examine interest in receiving contraception counseling and contraception initiation.
IND/IDE #	N/A
Study Population	Female adolescents 14 years and older hospitalized for mental health disorders at Nationwide Children’s Hospital.
Sample Size	N = 450
Study Duration for individual participants	5 months
Study Specific Abbreviations/ Definitions	
LARCs: long-acting reversible contraceptives LGBTQ: lesbian, gay, bisexual, transgender, queer EHR: electronic health record QI: quality improvement NCH: Nationwide Children’s Hospital

2.0 Objectives

2.1 The purpose of this study is to examine interest in receiving contraception counseling and contraception initiation female adolescents hospitalized with mental health disorders.

The primary objectives of this study are to 1) Examine interest in receiving contraception counseling among female adolescents hospitalized with mental health disorders, and 2) Examine contraception initiation among female adolescents hospitalized with mental health disorders.

Multiple secondary objectives will be investigated during the study. They include:

- To assess the proportion of female adolescents hospitalized with mental health disorders that receive contraception counseling or are prescribed/initiate any contraceptive during hospital admission or immediately post discharge.

- To determine predictors of receipt of contraception counseling and contraception initiation among female adolescents hospitalized with mental health disorders
- Assess satisfaction with and person-centeredness of contraception care among participants who received contraceptive counseling

2.2 State the hypotheses to be tested: N/A

2.3 Of note, this study is externally funded by Merck Inc. The PI has a conflict management plan in place approved by the compliance department.

3.0 Background

3.1 Approximately one in five American youth have experienced severe impairment due to mental health disorders, with anxiety and mood disorders being most common among female adolescents.¹ Mental health disorders are associated with a range of sexual risk behaviors and unintended pregnancy.^{2,3} Youth with mental health disorders have higher rates of condom and contraception non-use (especially short acting),^{2,4-6} earlier sexual debut,² and higher fertility rates.⁷

Avoiding an unwanted or unintended pregnancy is particularly important for women with underlying mental health disorders. Experiencing a pregnancy exacerbates underlying mental health disorders in women with mental health disorder.⁸ And children born out of an unintended pregnancy or in context of mother with active mental health disorder face additional risks to their wellbeing. Long-acting reversible contraceptives (LARCs), i.e., contraceptive implants and intrauterine devices, have attributes that may be particularly attractive to adolescents with mental health disorders. They are highly effective and do not require ongoing maintenance. However, adolescents with mental health disorders face multiple barriers to accessing contraception care. Novel solutions are needed to improve access to contraception care, including LARC, for adolescents with mental disorders.

The inpatient pediatric hospitalization setting is a missed opportunity for improving adolescent sexual and reproductive health.^{9,10} Nearly 10% of pediatric hospitalizations are for a primary mental health diagnosis, and mood disorders are the most common primary mental health diagnosis among these hospitalizations.^{11,12} Sexual and reproductive healthcare is rarely provided to hospitalized adolescents.

3.2 As part of the Hospital Pediatrics: Contraceptive Access Collaborative QI project at Nationwide Children's Hospital, a chart audit completed in December 2019 found that no adolescents hospitalized for mental health disorders on the Hospital Pediatrics service had documentation that they were screened for sexual activity.

3.3 Adolescents are interested in learning about sexual and reproductive health and receiving sexual and reproductive healthcare in the hospital setting regardless of age, gender, and prior sexual experiences.^{13,14} Two studies of pediatric hospitalists found that the majority of those physicians felt that sexual and reproductive services are appropriate for hospitalized adolescents, with high support for referrals and starting contraception in the hospital.^{15,16} Numerous barriers to inpatient provision of contraceptives/sexual reproductive healthcare were endorsed, including: concerns about follow up after discharge, lack of knowledge about confidentiality, lack of knowledge about contraception, interference with the treatment plan, time constraints, and pregnancy risk in LGBTQ youth. Riese et al.¹⁴ conducted a trial of an interactive patient-facing electronic sexual health module and found that it was acceptable to adolescents and their parents, and that most participants requested a sexual health service after completing the module. (The most requested service was viewing a contraception video made by this PI.)

4.0 Study Endpoints

4.1 The primary endpoints are interest in contraception and contraception initiation. Secondary endpoints are location of contraception counseling and initiation, and contraceptive method choice.

5.0 Study Intervention/Investigational Agent

5.1 The protocol here entitled “Evaluation of Contraception Care @ Behavioral Health Pavilion” describes how the investigators will examine interest in receipt of contraception counseling and initiation among female adolescents hospitalized with mental health disorders.

6.0 Procedures Involved*

6.1 This is an observational study. The study components include participant surveys, EHR data extracts related to sexual and reproductive health, and statistical process control charts for quality improvement analyses. Three surveys will be administered to participants, the first at the time of enrollment, the second immediately after discharge, and the third four months after discharge.

6.2 Potential participants will be approached during their admission at NCH and invited to participate in the study. If they are interested in participation, they will complete an electronic informed consent via redcap, all study participants will receive a copy of their consent via e-mail. If the participant is 14 years old the coordinator will be required to obtain verbal consent from the parent or guardian via Information Sheet. After the consent process is completed, they will fill out the first study survey while they are admitted to the hospital (see Appendix A). The

PROTOCOL TITLE: Evaluation of Contraception Care @ Behavioral Health Pavilion

subsequent two surveys will be sent electronically via their preferred communication method, which will be determined at enrollment. After the last survey is completed the subject will have completed their portion of the study. This is a study with adolescents as the study population and there will be little parental involvement, there are concerns regarding study retention. We will be providing texts as a communication option for the participants as we believe this will be most successful. If a participant chooses this as their preferred contact method. In order to text participants, we will be utilizing Twilio, an NCH approved application.

Study staff will review responses on the following questions on the baseline survey: if the participant indicates they would like to a) learn more about, b) initiate or change contraception methods, and c) desire for privacy for contraception care. Study staff will notify the patient's clinical team if any of these are positive.

On the day of discharge, or the first business day after discharge if participant is discharged during the weekend or a holiday, study staff will send the second survey (see Appendix B) to the participants who indicated interest in contraception counseling and initiation via their preferred communication method. The patient will have 1 month to complete the survey. They will receive weekly reminders if the survey is incomplete, and after 1 month the participant will be considered lost to follow up for the first follow-up survey. The third survey (see Appendix C) will be sent to the participants who indicated interest in contraception counseling and initiation 4 months after the patient is discharged from the hospital. Again, the participant will be provided the survey link via their preferred contact method and given 1 month to complete the survey and study staff will provide weekly reminders until completion. Completion of the third survey indicates the patient has completed their portion of the study. After 1 month, if the third survey is incomplete, the patient will be considered lost to follow up.

Additionally, routine data pulls from the electronic health record (EHR) will be generated to gather supplementary data not collected from the subject surveys (see Appendix D).

To ensure optimal readability, prior to the start of the enrollment period for the study we will be sending the surveys through the health literacy department. We will also pilot the surveys to 10-15 adolescent patients, ages 14 years and older, we would like to do this in order to get feedback on survey design, so that we can make necessary changes before enrollment starts. These patients may be approached in the Adolescent Medicine Clinic or may be children of NCH employees or other colleagues.

6.3 We do not anticipate any risks associated with enrollment in the study. All PHI and sensitive information recorded for research will only be available to study staff. Additionally, we will be requesting waived parental consent for participants 15 and older to mitigate any potential conflict between parent and participant due to the sensitive nature of this

study. Please see appendices A, B, and C and D for survey and data collection forms.

6.4 Once a participant enrolls in the study, they will then be prompted to complete the baseline survey (Appendix A).

Follow-up surveys will be completed by the participants that indicated interest in contraception counseling or initiation immediately following their discharge and an additional survey will be sent 4 months after discharge (Appendices B & C).

Additionally, EHR data will be collected (Appendix D) for information the participant may not be able to answer (insurance status, previous test results, unit census, etc.)

EHR data will be pulled to create variables for analysis and statistical process control charts to examine predictors of and receipt of contraception-related care among female adolescents 14 and older hospitalized for mental health disorders

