17.0 Data Management* and Confidentiality

17.1 *Describe the data analysis plan, including any statistical procedures or power analysis.*

For our first objective, the dependent variables are interest in receiving contraception counseling during a hospital stay and interest in starting a contraceptive during a hospital stay.

- We will examine interest in receiving contraception counseling during hospitalization among female adolescents hospitalized with mental health disorders by assessing the proportion of participants who answer yes to the following survey question “Interest in learning more about contraception during your hospital stay”.
- We will examine interest in initiating contraception during hospitalization among female adolescents hospitalized with mental disorders by assessing the proportion of participants who answer yes to the following question “Interest in starting a contraceptive during your hospital stay”.
- We will perform univariate descriptive analyses on all variables.
- We will perform bivariate analysis to explore the relationship between variables “Interest in learning more about contraception during your hospital stay” and “Interest in starting a contraceptive during your hospital stay” using 2 X 2 contingency tables.

PROTOCOL TITLE: Evaluation of Contraception Care @ Behavioral Health Pavilion

- We will explore associations with dependent variables and predictor variables by performing bivariate analyses of “Interest in learning more about contraception during your hospital stay” and “Interest in starting a contraceptive during your hospital stay” with predictor variables from surveys and EHR variables using Chi square for categorical variables and Students T-test for continuous variables.
- We will regress significant predictor variables ($p < 0.1$) on dependent variables to determine predictors of “interest in receiving contraception counseling during your hospital stay” and “interest in starting a contraceptive during your hospital stay”.

For our second objective the dependent variables are contraceptive prescription/initiation during hospitalization and contraceptive prescription/initiation following discharge.

- We will create derived variables:
 - Initiation any contraceptive (in hospital, in BC4Teens clinic, none)
 - Initiation preferred contraceptive (in hospital, in BC4Teens clinic, none)
 - Time interval (days) between enrollment and contraception prescription/initiation

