22.0 Setting

22.1 Describe the sites or locations where your research team will conduct the research.

- The research coordinator will be responsible for identifying and recruiting new subjects. They will screen the census each morning to determine patients that meet criteria. All recruitment activities will take place at NCH units as specified in the inclusion criteria.
- The enrollment questionnaire will be completed by the subject during their admission at NCH. The follow-up surveys will be sent to participants electronically after admission for them to complete on their own time; they will have one month to complete the follow-up surveys.

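### Section 6.2 sends surveys 2 and 3 to participants interested in counseling *and* initiation, section 6.4 says *or*, and the protocol does not say which rule governs

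*Combined protocol and SAP*

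**What the plan says.** Section 6.2 contains the two sending instructions. Survey 2 goes out at discharge "to the participants who indicated interest in contraception counseling and initiation via their preferred communication method". Survey 3 "will be sent to the participants who indicated interest in contraception counseling and initiation 4 months after the patient is discharged". Both require interest in counseling *and* initiation.

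Section 6.4 describes the same two surveys with the other conjunction: "Follow-up surveys will be completed by the participants that indicated interest in contraception counseling or initiation immediately following their discharge".

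Two overview statements carry no interest condition. Section 6.1 says "Three surveys will be administered to participants", and section 22.1 says "The follow-up surveys will be sent to participants electronically after admission for them to complete on their own time".

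The baseline questions that staff review (section 6.2) ask separately about learning more, about wanting to "initiate or change contraception methods", and about privacy. A positive answer to any one of them leads staff to notify the clinical team. Section 17.1 also keeps interest in learning more apart from interest in starting. Each has its own proportion, and of the pair it says "We will perform bivariate analysis to explore the relationship between variables", using a 2 x 2 table.

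One of the secondary objectives in section 2.1 is: "Assess satisfaction with and person-centeredness of contraception care among participants who received contraceptive counseling".

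**The concern.** The two conjunctions define different groups unless every participant answers both items the same way. Cross-tabulating the items only makes sense if answers can differ.

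The participant at issue asks to learn more but does not ask to start a method. Her answer triggers notification of the clinical team, so she may well be counseled. If she is, she belongs to the population named in the satisfaction objective. Under a literal reading of 6.2 she receives neither follow-up survey. The satisfaction and person-centeredness results would then describe only counseled participants who also wanted to start a method, and their views of the counseling may differ from those of participants who wanted information alone.

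A smaller gap exists under either rule: a participant counseled without having flagged any interest receives no follow-up survey, although the objective covers her too.

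**Working it through.** **The text side by side**

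| Place | Subject | Condition |
|---|---|---|
| 6.2, survey 2 | sending instruction | counseling AND initiation |
| 6.2, survey 3 | sending instruction | counseling AND initiation |
| 6.4 | both follow-up surveys | counseling OR initiation |
| 6.1, 22.1 | overview | none stated |
| 6.2, baseline review | notifying the clinical team | any flagged item positive |

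No sentence ranks these statements. The notification rule concerns clinical contact rather than survey mailing, so it supports OR without settling the matter.

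**The plan's own figure.** Sections 12.2 and 23.1 give 1,000 eligible adolescents and 45% agreement: 1,000 x 0.45 = 450, which matches the stated sample size. The documents give no size for the follow-up survey group and no rates for the two interest items.

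**How far apart the rules could be.** Let n = 450, p1 = share wanting to learn more, p2 = share wanting to start, and A = number saying yes to both.

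- AND group = A, which lies between max(0, n(p1 + p2 − 1)) and n x min(p1, p2)
- OR group = n(p1 + p2) − A
- Difference = n(p1 + p2) − 2A, which is at least n x |p1 − p2|
- Learn-more-only = n x p1 − A

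The rates below are assumptions, chosen only to show the range. Each range runs from greatest possible overlap to none.

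| Assumed learn / start | AND group | OR group | Difference | Learn-more-only |
|---|---|---|---|---|
| 25% / 25% | 112.5 to 0 | 112.5 to 225 | 0 to 225 | 0 to 112.5 |
| 35% / 25% | 112.5 to 0 | 157.5 to 270 | 45 to 270 | 45 to 157.5 |
| 45% / 25% | 112.5 to 0 | 202.5 to 315 | 90 to 315 | 90 to 202.5 |

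For example, at 35% / 25%, n x p1 = 157.5 and n x p2 = 112.5. Full overlap gives A = 112.5, so the difference is 270 − 225 = 45, all of it learn-more-only.

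The calculation assumes that all 450 answer both items, although section 18.1 lets participants skip questions. How many learn-more-only participants would be counseled is unknown, so these counts do not translate into a bias in satisfaction.

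**Compensation.** Section 13.4 pays $25 for each follow-up survey, so an added participant costs at most 2 x $25 = $50. Over the three cases, $50 x the difference is $0 to $11,250, $2,250 to $13,500, and $4,500 to $15,750.

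**The case against.** The strongest reply is that the *and* in 6.2 is loose drafting. The protocol pairs counseling and initiation as a topic label elsewhere (section 5.1, for example), 6.4 states the gate with *or*, and the notification rule responds to any single item. This largely stands: OR is probably what was meant. It does not dispose of the point, because the two sentences in 6.2 are the operative instructions and a coordinator could follow them as written.

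Harm is also conditional. Staff would have to apply AND literally, learn-more-only participants would have to exist and be counseled, and satisfaction would have to be measured only in surveys 2 and 3. The first three conditions are unknown. The last is a reasonable inference, since satisfaction with counseling is hard to ask about at enrollment, but the survey appendices are not shown. This objection stands too, and it is why no size of bias is claimed.

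The upper ends of the ranges require that nobody who wants to start a method also wants to learn more, which is implausible. They are arithmetic limits, not forecasts.

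A reader might also see sections 6.1 and 22.1 as a third, conflicting rule. They are overview statements and need not be read that way.

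**Conclusion.** The inconsistency is real and concerns a working rule: who receives two of the study's three surveys. It should be fixed, but its consequences are limited. The number of participants affected cannot be derived from the documents. It is zero if everyone answers both items alike, or if OR is what staff apply. Otherwise the two groups differ by at least 450 times the gap between the two yes rates. The exposed result is the secondary objective on satisfaction and person-centeredness, on the inference that it is measured in the follow-up surveys.

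Two stronger readings are tempting, and the documents support neither.

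- *The primary endpoints are compromised.* Interest comes from the baseline survey, which all participants are asked to complete. Section 24.0 lists prescription, initiation and discontinuation of contraception among the data available from the EHR. Neither endpoint is shown to depend on the survey gate.
- *The survey gate also defines who counts as interested in contraception care*, both in the section 17.1 initiation proportion and in the 25% remark in section 23.1. The visible text ties neither phrase to a baseline item, but it does not link them to the mailing rule either. That definition is a separate clarification. A combined any-item flag would be a lenient choice for the 25% remark: 15% on each of two non-overlapping items would count as 30%.

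**What to change.** 1. In both sentences of section 6.2, replace *and* with *or* to match 6.4, so that a yes to either learning more or initiating triggers surveys 2 and 3.
2. State whether a participant who wants only to change her method, which the second baseline item covers, meets this condition.
3. Report the satisfaction and person-centeredness results as covering interested participants who were counseled, because either gate misses anyone counseled without flagged interest.
4. Separately, define interest in contraception care for sections 17.1 and 23.1 on its own merits, without automatically adopting the survey gate.

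The overview text in 6.1 and 22.1 need not change, and surveying participants who flagged no interest is not required.

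The cost is mainly wording. Compared with a literal AND, each added participant costs up to $50 in compensation, plus the routine reminders. If OR was already intended, the first change adds nothing. Counting change-only participants could add some people, in a number the documents do not give. The third change makes the reported population slightly narrower than the objective as written, but accurate.

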7.0 Data and Specimen Banking*

- 7.1 The data will be kept for 3 years after completion of the study in order to complete data analysis. Through this time period the data will be kept on a password protected spreadsheet in a secure shared drive, only study staff will have access. At this time all data will be de-identified to ensure subject privacy.
- 7.2 List the data to be stored or associated with each specimen: N/A
- 7.3 No data containing PHI will be released. However, de-identified study data will need to be reported back to the study sponsor.

